### Residual Effect Period

The Residual Effect Period (REP) of BI 685509 is 7 days. This is the period after the last dose with measurable drug levels and / or pharmacodynamic (PD) effects still likely to be present.

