- patients with a QT or QTcF interval > 500 ms, or an increase of QT or QTcF of > 60 ms from the pre-dose value at Visit 2 / enrolment (baseline). Such cases must be reported as AEs
- the patient can no longer receive trial medication for other medical reasons such as surgery, AEs, other diseases
- the patient has not successfully completed the dose titration period (i.e. Visit 4), but has persistent AEs or severe effects requiring down-titration of the trial medication (refer to [Section 4.1.4.1](#))
- a female patient becomes pregnant. The patient will be followed up until birth or otherwise termination of the pregnancy. The data of the patient will be collected and reported in the Clinical Trial Report (CTR) until last patient last visit and any events thereafter will be reported in the BI Pharmacovigilance (PV) database (refer to [Section 5.2.6.2.3](#))

Trial-specific procedures have also been defined for Investigators to follow in case of increased liver enzymes (AST, ALT, and total bilirubin) after enrolment. For details refer to [Section 5.2.6.1.4](#) and [Appendix 10.2 \(P09-12413\)](#).

In the event of intolerance to BI 685509 after successful completion of the dose titration period at Visit 4 (e.g. persistent AEs despite two down-titrations, or severe effects at any dose), permanent treatment discontinuation should also be considered, based on Investigator judgement (refer to [Section 4.1.4.1](#)).

In addition to these criteria, the Investigator may discontinue patients at any time based on clinical judgement.

If a patient permanently discontinues the trial medications before the last allocated dose, an Early Discontinuation (ED) visit is required ideally within 7 days of discontinuing the medication. An EoS visit should be performed 4 weeks after the ED visit. Refer to Sections [6.2.2.1](#) and [6.2.3](#) for further details, including guidance with respect to trial assessments that should be included as part of an ED visit.

An individual patient will permanently discontinue empagliflozin if:

- Ketoacidosis is suspected.
- Fournier's gangrene is suspected.

If a patient in treatment arm 4 permanently discontinues empagliflozin or BI 685509, the patient must permanently stop the treatment with the other trial medication as well.

In the following cases, empagliflozin must be interrupted:

- Complicated UTI, including urosepsis
- Symptomatic volume depletion

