- ALT or AST increases  $> 2 \times$  baseline values and the increase is accompanied by a concomitant increase in total bilirubin to  $> 2 \times$  baseline value or INR concomitantly increases by  $> 0.2$  (to prevent false positive results, another sample should be tested within 24 hours)
- patient (with any magnitude of aminotransferase elevation) develops signs and symptoms of fatigue, nausea, vomiting, right upper quadrant pain or tenderness, fever, rash, and / or eosinophilia ( $> 5\%$ )

Proprietary confidential information © 2023 Boehringer Ingelheim International GmbH or one or more of its affiliated companies

Patients should be followed up until resolution of symptoms or signs in the above stated situations [\[P09-12413\]](#). After resolution or stabilisation the patient should complete the procedures for the EoT and EoS visits as outlined in the [Flow Chart](#), [Section 3.3.4.1](#) and Sections [6.2.2](#) and [6.2.3](#).

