## **6. GENERAL ANALYSIS DEFINITIONS**

### **6.1 TREATMENT(S)**

For basic study information on the treatment to be administered, assignment to treatment, and selection of dose, refer to CTP Section 4.

There will be three study phases in this trial: screening, study treatment phase (with avenciguat and avenciguat + empagliflozin) and follow-up.

Table 6.1: 1 Flow chart of analysis phases

Label	Interval	Start date	End date
Screening	Screening	Date of informed consent	Date of first administration of study medication -1
avenciguat [REDACTED] avenciguat [REDACTED] + empagliflozin 10mg	On-treatment	Date of first administration of study medication	Date of last intake of study medication + X*
Follow-up*	Follow up	Date of last intake of study medication + X* + 1	Latest of (day of EOS visit, last contact date on EOS page)

\*X=1, 3 or REP (7) days for safety laboratory, and AE respectively. X for other variables are defined in [Table 6.7: 1](#). Follow-up phase might not exist, e.g., if the patient's trial termination date is within 7 days after last administration of study drug.

The purpose of the definitions above is to describe all the different study/treatment intervals, to which a patient can be assigned during the course of the trial.

For efficacy analyses of HVPG, data up REP+1 (8 days) after last treatment intake will be considered as on-treatment, because an HVPG measurement at EOT is permitted within 7 days after scheduled EOT (i.e., REP+1 day after last dose) as stated in Section 5.1.1 of the CTP.

The efficacy analyses will follow the intention-to-treat (ITT) principle in assigning patients to treatment groups, i.e., patients will be analysed in the treatment group they were assigned or randomised to.

AEs with an onset during the time of the incorrect study treatment will be listed separately.

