## **6.7 BASELINE, TIME WINDOWS AND CALCULATED VISITS**

Regarding efficacy and safety endpoints, the term “baseline” refers to the last observed measurement prior to administration of any study medication.

Measurements taken prior to the first intake of study medication will be considered pre-treatment values. Pre-treatment values will be assigned to a visit according to the nominal visit number as recorded on the eCRF or as provided by the laboratory.

In general, the date of the first drug administration will be used to separate pre-treatment from on-treatment values. Measurements taken after first trial medication intake will be considered on-treatment values if they have been obtained up to end of the parameter specific follow-up period as defined in [Table 6.7:1](#) below and will be assigned to the corresponding study medication for efficacy and safety analyses.

Measurements taken after the end of the endpoint specific follow-up period will be considered post-treatment values.

Table 6.7: 1 Parameter specific follow-up period for the assignment to treatment phase

Endpoint	Last day of assignment to treatment phase (days after study medication stop date)
Efficacy	
HVPG	8 (REP + 1)
A large black rectangular box used to redact sensitive information.	
Safety	
Adverse events	7
Safety laboratory measurements	3
Vital signs (including body weight, blood pressure)	1

For derivation of the last value on treatment, minimum value on treatment, and maximum value on treatment, all values from the relevant phase (whether or not collected in any time window; see [Table 6.1:1](#) for definition of the trial phases) will be considered; these will be derived for analysis of laboratory and vital signs data. For identification of potentially clinically significant abnormal laboratory values, all values (whether selected in any time window) up to 7 days after last treatment intake will be considered.

On-treatment efficacy, safety [REDACTED] measurements will be assigned to visits based on the extended time windows around the planned visit dates, defined relative to the day of first trial medication intake (see [Table 6.7:2](#)).

Table 6.7: 2 Time windows for assignment of measurements to visits for statistical analysis

Visit number /name	Visit label	Planned day B	Time window (Days)				
			Window (per CTP)	Start (per CTP)	End (per CTP)	Start (extended)*	End A (extended) #
V1	Screening	-42				-∞	0
On-treatment							

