### **7.8.1 Laboratory data**

The analyses of laboratory parameters will be descriptive in nature and will be based on BI standards (7). Note that data from the central Laboratory will be used for all displays described below, unless otherwise specified.

For continuous safety laboratory parameters standardized and normalized values will be derived as well as the differences to baseline. Normalisation means transformation to a standard unit and to a standard reference range. The process of normalisation, handling of repeat values at the same visit for by-visit displays, as well as standard analyses for safety laboratory data are described in the BI guidance for “Handling, Display and Analysis of Laboratory Data” (7). All analyses considering multiple times of the ULN (as described below) will be based on standardised and not normalised values.

Laboratory parameters will be shown in conventional units. Where conventional units differ from SI units, analyses will be repeated on SI units in the appendix.

Laboratory values will be compared to their reference ranges and frequency tables will be provided for the number of patients within and outside the reference range at baseline and the last measurement on treatment. Descriptive statistics will be provided by treatment group and total for baseline, last value on-treatment and for changes from baseline to last value on treatment. Frequency tables will summarise the number of patients with potentially clinically significant abnormalities.

Both on-treatment and post-treatment values of the following lab parameters will be presented graphically. The values after the treatment period will be assigned to the follow-up (EoS) period.

- Haematocrit
- Haemoglobin
- RBC count / erythrocytes
- WBC / leukocytes
- Platelet count / thrombocytes
- Reticulocytes
- INR
- ALT
- Alkaline phosphatase
- AST
- Bilirubin (total)
- Albumin
- gamma-GT
- eGFR

Only patients with at least one available on-treatment value will be included in the analysis of an individual laboratory parameter. All individual data will be presented in listings.

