To support analyses of liver related adverse drug effects, the frequency of patients with AST and/or ALT  $\geq$  3xULN combined with the total bilirubin  $\geq$  2xULN in a 30-day period after AST/ALT elevation will be displayed, stratified by alkaline phosphatase  $<$  2xULN and  $\geq$  2xULN (a patient can potentially be in both alkaline phosphatase strata in case of multiple AST/ALT and bilirubin elevations). The start of the 30-day time span is triggered by each liver enzyme elevation above defined thresholds. This analysis will be based on standardised laboratory values.

A graphical analysis of the ALT and total bilirubin during the on-treatment period will also be performed; the so called eDISH plot. In the graph, for each subject, the peak total bilirubin is presented as a fold increase over the ULN against the peak ALT as a fold increase over the ULN, on a log 10 scale. The measurements displayed for total bilirubin and ALT may, or may not, occur on the same date. Two reference lines, 2xULN for total bilirubin and 3xULN for ALT, are drawn onto the graph to divide the plane into four quadrants. Normal cases are in the lower left quadrant, potential DILI cases are in the upper right quadrant (Hy's Law quadrant), while the lower right quadrant is known as the Temple's corollary range (ALT  $\geq$  3xULN and total bilirubin  $<$  2xULN). The same graphical analysis will be performed for AST and total bilirubin during the on-treatment period as well. Details on patients with elevated liver enzymes will be listed.

Clinically relevant findings in laboratory data will be reported as baseline conditions (at screening) or as AEs (during the trial). If judged clinically relevant by the investigator and will be analysed as such.

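### The eDISH plots stop counting liver values 3 days after the last dose, although the residual effect period and the plan's own rule for significant laboratory abnormalities are 7 days

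*SAP*

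**What the plan says.** SAP 7.8.1 plans an eDISH plot: "A graphical analysis of the ALT and total bilirubin during the on-treatment period will also be performed". Each subject is placed by peak ALT and peak total bilirubin, as multiples of ULN, with reference lines at 3xULN and 2xULN. A second plot does the same with AST.

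The meaning of on-treatment comes from SAP 6.1 and 6.7. Table 6.7:1 sets the days after the stop date: 3 for safety laboratory, 7 for adverse events, 1 for vital signs and 8 for HVPG. The on-treatment maximum is taken from all values in that phase. Beyond it, "Measurements taken after the end of the endpoint specific follow-up period will be considered post-treatment values", and SAP 7.8.1 adds: "The values after the treatment period will be assigned to the follow-up (EoS) period". The footnote to Table 6.1:1 reads: "X=1, 3 or REP (7) days for safety laboratory, and AE respectively".

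Two further rules matter. SAP 6.7 uses values up to 7 days after the last intake to identify potentially clinically significant laboratory abnormalities. SAP 7.8.1 includes a patient in the analysis of a laboratory parameter only if at least one on-treatment value exists.

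In the protocol, section 1.2.1 states: "The Residual Effect Period (REP) of BI 685509 is 7 days". Section 1.2.2 gives the same length for empagliflozin. Section 3.3.4.1 says of early stops: "Early Discontinuation (ED) visit is required ideally within 7 days of discontinuing the medication". The Flow Chart places a safety laboratory sample at that visit.

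**The concern.** An ED sample on days 4 to 7 after stopping complies with the protocol and lies within the period in which the protocol still expects drug levels or effects. The SAP nevertheless treats it as post-treatment, so it cannot contribute to the eDISH peak. The patients affected are those who stop early, including those stopped for hepatic injury, and these are the patients a drug-induced liver injury display most needs to place correctly.

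The SAP also applies two windows to the same liver values: 7 days for significant abnormalities and 3 days for the plot. For HVPG it chose 8 days precisely because the protocol allows a late measurement. It did not apply that reasoning to the ED laboratory sample.

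**Working it through.** The plan gives no figure to reproduce, so the check sets the windows side by side and follows patients through them.

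**Inputs.** Laboratory window 3 days, adverse event window 7 days and abnormality rule 7 days (SAP 6.7); residual effect period 7 days (Protocol 1.2.1, 1.2.2); ED visit within 7 days of stopping (Flow Chart footnote 3; ideally so in Protocol 3.3.4.1 and 6.2.2.1); last BI 685509 dose on the evening before a regular end-of-treatment (EoT) visit (Protocol 4.1.4).

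| Sample, days after last dose | eDISH peak | Significant-abnormality rule | Adverse event window |
|---|---|---|---|
| +1 (regular EoT) | in | in | in |
| +2 to +3 | in | in | in |
| +4 to +7 (ED sample allowed) | out | in | in |

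The gap is 7 - 3 = 4 days, namely days +4, +5, +6 and +7.

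**Patient A, wrong quadrant.** ALT is at least 3xULN when the drug is stopped. Bilirubin is below 2xULN through day +3 and first reaches 2xULN on day +5. With the 3-day window, the plotted peaks are ALT at or above 3xULN and bilirubin below 2xULN, which is the lower right (Temple's corollary) quadrant. With a 7-day window, bilirubin is at or above 2xULN and the patient moves to the upper right (Hy's Law) quadrant. SAP 7.8.1 also counts patients whose bilirubin reaches 2xULN "in a 30-day period after AST/ALT elevation will be displayed", with no stated on-treatment cut-off. Patient A can therefore be a case in that table and not in the plot.

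**Patient B, no on-treatment value.** The last dose is on Day 4 and the ED visit on Day 9, which is day +5. The laboratory period ends on Day 4 + 3 = Day 7; the residual effect period ends on Day 4 + 7 = Day 11. The Visit 2 sample is drawn before the first dose and is pre-treatment. The ED visit takes the place of Visit 3, and its sample on Day 9 is post-treatment. Without an unscheduled sample in between, there are no on-treatment values, and the inclusion rule in SAP 7.8.1 leaves the patient out. The SAP does not say whether the 7-day abnormality rule overrides the inclusion rule for such a patient.

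**Footnote.** Table 6.1:1 lists three values (1, 3, 7) and names two items (safety laboratory, adverse events). Read in order, the first value would give laboratory 1 day. Table 6.7:1 shows that 3 and 7 are meant and that 1 belongs to vital signs.

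**The case against.** The strongest reply is that little is lost. Values from days 4 to 7 still feed the significant-abnormality tables. All individual data are listed, as are details of patients with elevated liver enzymes. Hepatic injury is an adverse event of special interest, adverse events count for 7 days, and certain hepatic events are adjudicated. The trial plans no hypothesis test. This stands, and it sets the size of the point: a reader should not infer that liver signals disappear from the report.

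A second reply is that 3 days is pharmacologically reasonable. With a half-life of 9 to 15 hours (Protocol 1.2.1), 72 hours is 72/15 = 4.8 to 72/9 = 8 half-lives, leaving about 3.6% to 0.4% of the drug. That supports a short window for mean summaries. It does not settle a safety plot, because the protocol's 7-day period also covers pharmacodynamic effects.

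Five stronger readings are tempting, and the documents do not support them:

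- *Most ED samples are lost.* Four of the seven days lie past the cut, but nothing states how ED visits spread over those days or how many patients stop early. No share or count can be given.
- *Liver cases have long gaps without on-treatment values.* Visit 6 has no safety laboratory sample, so a patient stopping on Day 40 may have Day 29 as the last scheduled value. Appendix 10.2, however, calls for repeat tests within 48 to 72 hours, and unscheduled values up to day +3 count towards the peak. The gap fits a stop for non-hepatic reasons better.
- *An ED value is displayed as Week 12.* With a stop on Day 40 and ED on Day 45, the end-of-study (EoS) visit falls on Day 45 + 28 = Day 73. The selection rule in SAP 6.7 prefers the value nearest Day 85: Day 73 is 12 days away and Day 45 is 40. The rule is written for on-treatment visits, but footnote A of Table 6.7:2 says off-treatment values are assigned in the same manner. Mislabelling is likely only if the EoS sample is missing.
- *The plot should share the 30-day bilirubin search.* That search starts from an enzyme elevation. The plot includes every subject, and those without an elevation have no start date.
- *Appendix 10.2 breaks the ED rule.* It says "After resolution or stabilisation the patient should complete the procedures for the EoT and EoS visits", which sits awkwardly with a visit within 7 days. Because that timing is only ideal in two sections, the conflict is soft, and it is separate from the analysis window.

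**Conclusion.** The point holds in limited form. As written, the SAP leaves out of both eDISH plots any ALT, AST or bilirubin peak on days 4 to 7 after an early stop, and it can exclude a very early discontinuer from a parameter's analysis. This departs from the residual effect period, the adverse event window and the SAP's own 7-day abnormality rule. The consequence is misplaced or absent points on a descriptive safety display, together with thinner on-treatment laboratory summaries, for early discontinuers only. Patients who complete treatment and give their EoT sample on day +1 are not affected.

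The conclusion assumes that on-treatment in SAP 7.8.1 carries the meaning of Tables 6.1:1 and 6.7:1; the SAP offers no other. The number of patients is unknown, because the documents give no early-stop rate, no distribution of ED timing and no rate of liver elevation. The change is worth making because it is cheap and concerns the main display for drug-induced liver injury, not because a large loss of data has been shown.

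**What to change.** 1. In SAP 7.8.1, state that the ALT and AST eDISH plots use peaks from first dose to last dose + 7 days (REP).
2. For the rule that a patient needs at least one on-treatment value, count laboratory values in that same window.
3. Correct the Table 6.1:1 footnote so that each value is tied to a named parameter and agrees with Table 6.7:1.
4. The 3-day window may stay for the last-on-treatment mean summaries. If so, state that a patient whose only value falls on days 4 to 7 contributes to the plots and abnormality tables but not to those means.

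The cost is SAP wording and one programming parameter, with no new data. The downside is that a few values taken 4 to 7 days off drug enter the plots.

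Separately, the sponsor should reconcile the visit timing in Appendix 10.2 with the 7-day ED timing elsewhere in the protocol. The change above does not depend on how that is resolved.

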### 3.3.3 Exclusion criteria

1. Previous clinically significant decompensation events (e.g. ascites [more than perihepatic ascites], VH and / or overt / apparent HE)
2. History of other forms of chronic liver disease (e.g. alcohol-related liver disease (ARLD), autoimmune liver disease, primary biliary sclerosis, primary sclerosing cholangitis, Wilson's disease, haemachromatosis, alpha-1 antitrypsin [A1AT] deficiency)
3. Patients without adequate treatment for HBV, HCV or NASH as per local guidance (e.g. antiviral therapy for chronic HBV or HCV infection or lifestyle modification in NASH)
  - if received curative anti-viral therapy for HCV, no sustained virological response (SVR) or SVR sustained for less than 2 years prior to screening or if HCV RNA detectable
  - If receiving anti-viral therapy for HBV, less than 6 months on a stable dose prior to screening, with planned dose change during the trial or HBV DNA detectable
  - Weight change  $\geq 5\%$  within 6 months prior screening
4. Must take, or wishes to continue the intake of, restricted concomitant therapy (refer to [Section 4.2.2.1](#)) or any concomitant therapy considered likely (based on Investigator judgement) to interfere with the safe conduct of the trial
5. SBP  $< 100$  mmHg and DBP  $< 70$  mmHg at screening (Visit 1a)

---

A woman is considered of child-bearing potential, i.e. fertile, following menarche and until becoming post-menopausal unless permanently sterile. Permanent sterilisation methods include hysterectomy, bilateral salpingectomy and bilateral oophorectomy. Tubal ligation is NOT a method of permanent sterilisation. A post-menopausal state is defined as no menses for 12 months without an alternative medical cause

Proprietary confidential information © 2023 Boehringer Ingelheim International GmbH or one or more of its affiliated companies

6. Model of End-stage Liver Disease (MELD) score of > 15 at screening (Visit 1a), calculated by the central laboratory
7. Hepatic impairment defined as a Child-Turcotte-Pugh score  $\geq$  B8 at screening (Visit 1a), calculated by the site, using central laboratory results (refer to [Appendix 10.3](#))
8. ALT or AST  $>$  5 times upper limit of normal (ULN) at screening (Visit 1a), measured by the central laboratory
9. eGFR (CKD-EPI formula)  $<$  20 mL/min/1.73 m^2 at screening (Visit 1a), measured by the central laboratory

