## **10. APPENDICES**

## **10.2 REMOVAL OF INDIVIDUAL PATIENTS IN CASE OF INCREASED LIVER ENZYMES**

Trial-specific procedures have been defined in case of increased liver enzymes after enrolment as outlined below. Baseline refers to Day 1.

- **Normal aminotransferases at baseline**

New elevations of aminotransferases to  $> 2 \times$  ULN should be followed by a repeat testing within 48 to 72 hours. If elevations persist, other causes of aminotransferase elevations should be evaluated along with tests of hepatic function. If no other cause is identified, the patient should be monitored closely.

Treatment with trial medication should be discontinued if:

- ALT or AST increases to  $> 8 \times$  ULN
- ALT or AST increases to  $> 5 \times$  ULN for more than 2 weeks
- ALT or AST increases to  $> 3 \times$  ULN and the increase is accompanied by a concomitant increase in total bilirubin to  $> 2 \times$  ULN or INR to  $> 1.5$
- ALT or AST increases to  $> 3 \times$  ULN and the increase is accompanied by the appearance of fatigue, nausea, vomiting, right upper quadrant pain or tenderness, fever, rash, and / or eosinophilia ( $> 5\%$ )

- **Abnormal aminotransferases at baseline**

If a patient develops elevations of ALT or AST to  $> 2 \times$  baseline or total bilirubin  $1.5 \times$  baseline values, the testing should be repeated within 48 to 72 hours. If elevations persist, then close observation (testing and physical examination 2 to 3 times a week) should be implemented and discontinuation of trial medication should be considered. Decision to discontinue the trial medication should be considered based on factors that include how much higher than baseline ALT and AST values were relative to ULN and how much the on-treatment ALT and AST values have increased relative to baseline, in addition to the elevation of total bilirubin or INR.

Treatment with trial medication should be discontinued if:

- baseline values were  $< 2 \times$  ULN, and ALT or AST increases to  $> 5 \times$  baseline values
- baseline values were  $\geq 2 \times$  ULN but  $< 5 \times$  ULN, and ALT or AST increases to  $> 3 \times$  baseline values
- baseline values were  $5 \times$  ULN, and ALT or AST increases to  $> 2 \times$  baseline values

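### The two dedicated liver displays in SAP 7.8.1 have no baseline reference, so stable baseline disease can plot as potential DILI and a rise meeting Appendix 10.2 can plot as normal

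*SAP*

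**What the plan says.** SAP 7.8.1 (Laboratory data) specifies two displays aimed at drug-related liver injury.

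- A frequency count of patients with AST and/or ALT at or above 3xULN and total bilirubin at or above 2xULN within 30 days after the enzyme elevation, split by alkaline phosphatase.
- eDISH plots over the on-treatment period, in which "the peak total bilirubin is presented as a fold increase over the ULN against the peak ALT as a fold increase over the ULN". "Two reference lines, 2xULN for total bilirubin and 3xULN for ALT, are drawn onto the graph to divide the plane into four quadrants". The reading given is: "Normal cases are in the lower left quadrant, potential DILI cases are in the upper right quadrant". The two peaks need not coincide: "The measurements displayed for total bilirubin and ALT may, or may not, occur on the same date". The plot is repeated for AST.

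Protocol 3.3.3 sets the liver-related entry limits. ALT or AST is excluded only above "5 times upper limit of normal (ULN) at screening (Visit 1a), measured by the central laboratory". There is no separate bilirubin criterion. Bilirubin is limited indirectly, by excluding a Child-Turcotte-Pugh score at or above "B8 at screening (Visit 1a), calculated by the site, using central laboratory results" and a MELD score above "15 at screening (Visit 1a), calculated by the central laboratory".

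Protocol Appendix 10.2 treats patients according to their Day 1 aminotransferases. With normal values, its criteria are multiples of ULN. Under "Abnormal aminotransferases at baseline" they become multiples of the patient's own baseline. One of these is a paired criterion: ALT or AST above 2x baseline together with total bilirubin above 2x baseline, or with an INR rise of more than 0.2.

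**The concern.** The protocol recognises that some patients will start with abnormal liver tests and judges them against their own baseline. The two SAP displays judge everyone against ULN. For patients with normal baseline aminotransferases this agrees with Appendix 10.2, which also pairs 3xULN with 2xULN bilirubin. For patients with abnormal baseline aminotransferases it does not, and the mismatch can run both ways: an unchanged patient can look like a case, and a changed patient can look normal.

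This matters more here than in a placebo-controlled trial. Every treatment group receives BI 685509 (avenciguat in the SAP) and there is no placebo arm (Protocol 3.2). No untreated group shows how often stable cirrhosis alone puts a patient above both lines, so the patient's own baseline is the only reference within the trial.

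**Working it through.** The plan gives no figure on this point to reproduce. The check has four steps.

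**1. Bilirubin values that may enter.** In the Child-Turcotte-Pugh table (Protocol Appendix 10.3), bilirubin below 2, 2 to 3, and above 3 mg/dL scores 1, 2 and 3 points. With the other four items at 1 point each:

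- 2 to 3 mg/dL: 2 + 4 = 6 points, class A, eligible on this criterion.
- Above 3 mg/dL: 3 + 4 = 7 points, B7, still below the B8 exclusion.

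The MELD limit also applies. The documents do not give its formula, so it was not converted into a bilirubin value.

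**2. Comparison with the 2xULN line.** The documents do not give the bilirubin ULN. For an assumed ULN of 1.0 to 1.5 mg/dL, 2xULN is 2.0 to 3.0 mg/dL, which lies within the band that a class A patient may have. ALT or AST from 3xULN to 5xULN is also allowed. A patient can therefore be at or above both lines before the first dose.

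**3. Illustrative patients on both scales.**

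| Patient | ALT, xULN (baseline to peak) | Bilirubin, xULN (baseline to peak) | SAP eDISH quadrant | Multiples of baseline (ALT; bilirubin) | Appendix 10.2 laboratory criterion |
|---|---|---|---|---|---|
| A, stable | 3.5 to 3.5 | 2.1 to 2.1 | Upper right: potential DILI | 1.0; 1.0 | None met |
| B, rising | 1.2 to 2.6 | 0.8 to 1.7 | Lower left: normal | 2.6/1.2 = 2.2; 1.7/0.8 = 2.1 | Paired criterion met |
| C, rising | 2.0 to 4.5 | 0.9 to 1.9 | Lower right | 4.5/2.0 = 2.25; 1.9/0.9 = 2.1 | Paired criterion met |

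Patients B and C are also missed by the combined count, because bilirubin stays below 2xULN. The table takes the ALT and bilirubin rises in B and C as concomitant, as the criterion requires.

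**4. How many patients could resemble A.** The documents give no baseline distribution of liver tests, so the proportion p above both lines at baseline is an assumption. For the planned 80 patients, the expected number is 80p and the chance of at least one is 1 - (1 - p)^80.

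| Assumed p | Expected number | Chance of at least one |
|---|---|---|
| 0.5% | 0.4 | 33% |
| 1% | 0.8 | 55% |
| 2% | 1.6 | 80% |
| 5% | 4 | 98% |
| 10% | 8 | about 100% |

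This range shows what would follow from each assumption. It is not an estimate of the frequency.

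**The case against.** The strongest reply is that these two displays are screening tools among several liver outputs. SAP 7.8.1 also plans change from baseline to the last on-treatment value, reference-range tables at baseline and last value, graphs of ALT, AST and total bilirubin, and listings, including one of patients with elevated enzymes. SAP 7.8.2.4 takes the definition of hepatic injury from Appendix 10.2, baseline multiples included, and tabulates events adjudicated for causal relationship. The laboratory analyses are descriptive, and no endpoint or stopping decision depends on the plots. The SAP also defers its standard laboratory analyses to a sponsor guidance document that is not available here and may add outputs.

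Much of this stands, and it limits the point. A reader might infer any of the following, which the documents do not support:

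- *That baseline disease fills the potential-DILI quadrant.* A patient must exceed both limits, and detectable HBV DNA or HCV RNA is excluded. At least 40 of the 80 patients are to have NASH, where the viral rules do not bear on disease activity, but that does not establish a frequency.
- *That all liver-safety outputs ignore baseline.* Only the combined count and the eDISH plots do.
- *That a patient doubling from 4xULN to 8xULN is hidden.* The axes are continuous, so the peak plots at 8xULN. Exactly 2x baseline also does not exceed any ALT multiple in Appendix 10.2.
- *That Appendix 10.2 applies baseline multiples to anyone with raised bilirubin.* That section covers abnormal aminotransferases only.

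What the reply does not remove is a narrow gap. Change to the last value loses a peak that has settled. The hepatic injury and adjudication tables present events and preferred terms. Listings leave the comparison to the reader. No specified output sets peak against baseline.

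**Conclusion.** The point holds in limited form. The combined count and the eDISH plots have no baseline reference. The entry criteria allow a patient to be above both lines before dosing, and a rise that meets the protocol's paired criterion can fall in the quadrant described as normal. The entry example rests on an assumed bilirubin ULN of 1.0 to 1.5 mg/dL and on the patient also having MELD of 15 or less, which could not be checked. The number of patients affected is unknown.

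No endpoint or treatment estimate changes. What changes is which patients the planned liver displays pick out, in a trial with no untreated arm. That makes this a worthwhile, inexpensive improvement to the SAP. It is not a flaw in the trial's conclusions.

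**What to change.** Keep the ULN displays and add the following to SAP 7.8.1.

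1. Mark each patient's baseline position on the eDISH plots, and give a baseline-to-peak quadrant shift table for ALT and for AST.
2. For patients with abnormal baseline aminotransferases, add an eDISH plot and a combined count on multiples of baseline, with reference lines at 2x baseline ALT or AST and 2x baseline bilirubin. These are the limits of the paired criterion already in Appendix 10.2.
3. Tabulate the number of patients meeting each Appendix 10.2 laboratory criterion, including the INR part of the paired one, by normal or abnormal baseline aminotransferases. Patients with raised bilirubin but normal aminotransferases stay under the ULN criteria, as in the appendix.
4. State in the SAP which interval counts as concomitant for the paired criterion. The eDISH peaks may come from different dates, so the plot alone cannot show this.

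The data are already collected. The cost is a few extra figures and tables. No stopping rule or clinical management changes.
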